17.5 Additional analyses

An additional evaluation of the primary endpoint will be made, including actual concizumab dose level as *additional factor in the primary analysis model specified above*. Point estimates and 95% confidence interval will be provided for the ABR at the different dose levels of concizumab (0.15, 0.20 and 0.25 mg/kg). Furthermore, an analysis with individual steady state PK/PD assessments included as covariates in the negative *binomial regression model as specified for the primary analysis* will be performed in order to evaluate possible associations between PK/PD and ABR that potentially could guide dose-selection. The referred steady-state PK/PD assessments comprise the concizumab trough level, maximum plasma concentration (C_{max}) of concizumab, TFPI value prior to the last s.c. dose administration, peak thrombin generation (nM), Endogenous thrombin potential (nM*min) and velocity index (nM/min).

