Endpoints comprising number of bleeding episodes will be evaluated based on treated bleeding episodes only. Multiple bleeding locations occurring from the same event (e.g., due to a bicycle accident) or at the same time point will be counted as one bleeding episode. Further, the endpoints will not include re-bleed.

A re-bleed is defined as a bleeding episode (worsening of bleeding site conditions e.g. swelling, pain) within 72 hours after stopping treatment of a previous bleeding episode at the same (or subset of the same) anatomical location. If a bleeding episode occurs in the same location 72 hours after stopping treatment, the bleed is defined as a new bleeding episode.

Clinical proof of concept

The statistical analysis of the collected data aims to establish CPoC that concizumab is efficacious in preventing bleeding episodes in haemophilia A patients without inhibitors. The objective will be assessed when the last of the 30 patients have completed 24 weeks of dosing (or have withdrawn).

Two criteria will be evaluated in a hierarchical fashion in support of CPoC comprising a comparison of the ABR of all patients with a threshold of 12, irrespective of individual dose titration. The primary CPoC criterion aims at evaluating the effect of concizumab at the last dose level reached for a patient. Hence, for this evaluation, only observations from the period where patients are on their end dose at time of analysis will contribute to the analysis. Furthermore, observations from the 2 week run-in period will be not be included. Since this evaluation disregards a subset of data collected the result should be viewed taking in to account the potential bias. The second CPoC criterion aims at evaluating the effect of concizumab when given as an escalation regimen. Hence, this will compare the ABR of haemophilia A patients treated with concizumab with the typical historical ABR of haemophilia A patients being treated on-demand using all data after enrolment. The second CPoC criterion will only be evaluated if the first one succeeds.

Protocol
 Trial ID:NN7415-4255
 UTN:U1111-1179-3872
 EudraCT no.:2016-000614-29

~~CONFIDENTIAL~~

Date: 18 December 2017
 Version: 3
 Status: Final
 Page: 100 of 124
 Novo Nordisk

The referred comparisons will be made using a negative binomial model with log of *exposure time in main phase* as offset. For each criterion, evidence of effect will be concluded if the 95% confidence interval of the estimated ABR is below 12.

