17.1 Sample size calculation

The sample size calculation has been determined taking the small patient population into account, while also aiming for an acceptably narrow 95% confidence interval for the ABR.

Sufficient inference on bleeding episodes for the primary CPoC criterion is judged to be accommodated by 30 patients.

It is expected that the treatment duration of the main part allowing for escalation time for some patients is on average 6 months in the below calculations.

When evaluating the power of the negative binomial analysis referred above, an annual bleeding rate of 4 is assumed for the end dose concizumab regimen, respectively in combination with an over-dispersion of 6. The power for concluding a bleeding rate lower than 12 then becomes approximately 95%. The power under varying values of true ABR and over-dispersion for the primary CPoC criterion are shown below in [Table 17–1](#).

Table 17–1 Power in comparison between concizumab prophylaxis treatment and an ABR threshold of 12 under different assumptions of ABR and over-dispersion.

Power	Over-dispersion		
	5	6	7
4	99%	95%	92%
5	95%	90%	86%
6	87%	81%	72%

Protocol
 Trial ID:NN7415-4255
 UTN:U1111-1179-3872
 EudraCT no.:2016-000614-29

~~CONFIDENTIAL~~

Date:	18 December 2017	Novo Nordisk
Version:	3	
Status:	Final	
Page:	101 of 124	

For the secondary CPoC criterion that includes data prior to potential dose escalation, it is expected that the treatment duration of the main part is on average 8 months with an average ABR of 5.4 for the concizumab treated patients. This yields a marginal power of approximately 87% for the secondary CPoC criterion.

In prior Novo Nordisk trials conducted in haemophilia patients, the typical 1-year over-dispersion for non-inhibitor patients on prophylaxis with FVIII or FIX has been in the range 4-8, implying 24 weeks over-dispersion of 3-5 (e.g. in NN7008-3543, NN7088-3859 and NN7999-3747). On that background, an over-dispersion of 6 over the 24 weeks in the main part of the current trial is deemed realistic.

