17.8 Interim analysis

The trial does not include a formal interim analysis. However, the split of the trial into a main and extension part offers the opportunity of reporting results before the end of the trial. Other reporting of the trial might be done during the extension part once the data collection and review of the main part data has been finalised and individual clinical study reports might in such case be issued. A final clinical study report describing results from the main and extension part will be written when the last patient has either completed or withdrawn from the trial.

All main conclusions regarding clinical proof of concept and dose guidance for phase 3 will be based on the reporting after the main part, see [Figure 17-1](#).

[figure not shown]

Figure 17-1 Definition of main and extension part

Protocol
 Trial ID: NN7415-4255
 UTN: U1111-1179-3872
 EudraCT no.: 2016-000614-29

~~CONFIDENTIAL~~

Date:	18 December 2017	Novo Nordisk
Version:	3	
Status:	Final	
Page:	107 of 124	

18 Ethics

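### Section 17.5 estimates bleeding rates by dose in a model with no patient term, although patients reach the higher doses only because they bled

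*Protocol*

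**What the plan says.** References to Section 17 are to protocol version 3, because the version 4.0 text at hand stops before it. The escalation rule in 5.3.1 is the same in both versions.

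- **Primary model (17.3).** Negative binomial regression with log main-phase exposure as offset. No patient effect, bleeding history or other covariate is named.
- **Dose analysis (17.5).** The primary endpoint is analysed again, "including actual concizumab dose level as *additional factor in the primary analysis model specified above", with an ABR and 95% interval for each of the three doses.
- **PK/PD analysis (17.5).** Individual steady-state values enter the same model as covariates, "in order to evaluate possible associations between PK/PD and ABR that potentially could guide dose-selection". Only the TFPI value is tied to the last dose. The section does not say whether there is one record per patient or per dose period, or which bleeds each value is paired with.
- **How dose is reached (5.2, 5.3.1).** Everyone starts at 0.15 mg/kg. A step up requires at least three treated spontaneous bleeds in the preceding 12 weeks, after a 2-week run-in, with counting restarted at each step.
- **Use (17.8).** "All main conclusions regarding clinical proof of concept and dose guidance for phase 3 will be based on the reporting after the main part".
- **Caveat.** The one remark on potential bias, in the proof-of-concept text of Section 17, concerns the last-dose criterion and not 17.5.

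**The concern.** Dose is a consequence of the outcome. Time at 0.20 and 0.25 mg/kg comes only from patients who bled often, while time at 0.15 mg/kg comes from everyone. With no patient term, the model has nowhere to put the difference between patients except the dose factor. The over-dispersion of 6 assumed in 17.1 means those differences are large.

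The same mechanism affects the PK/PD covariates. An escalated patient tends to have a higher end-dose concentration. If that value is paired with all main-part bleeds, it is set against the bleeds at the lower dose that caused the escalation.

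At stake is what the main-part report says about dose and exposure ahead of phase 3. Section 17 expects a steep dose response, and this model could conceal it. The protocol names the model, so this is a stated choice and not a detail left open for the SAP.

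**Working it through.** **1. The plan's own power figures, to fix the meaning of over-dispersion.**

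Inputs: the decision rule in Section 17 ("evidence of effect will be concluded if the 95% confidence interval of the estimated ABR is below 12"), and from 17.1 n = 30 ("Sufficient inference on bleeding episodes for the primary CPoC criterion is judged to be accommodated by 30 patients"), T = 0.5 year ("is on average 6 months in the below calculations"), ABR 4 and over-dispersion 6 ("an annual bleeding rate of 4 is assumed for the end dose concizumab regimen, respectively in combination with an over-dispersion of 6"). Take over-dispersion as φ = variance/mean, with negative binomial k = (φ − 1)/μ.

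- μ = 4 × 0.5 = 2. Approximate se of the log rate = √(φ/(nμ)) = √(6/60) = 0.316. Then ln(12/4)/0.316 − 1.96 = 1.51, so power ≈ 93.5%.
- Simulating the maximum-likelihood fit with a Wald interval gives 96.1% against the stated 95%. All nine cells of Table 17-1 reproduce within 2 points.
- Secondary criterion ("with an average ABR of 5.4 for the concizumab treated patients"): k = 5/(5.4 × 0.5) = 1.85. Over 8 months, φ = 1 + 1.85 × 3.6 = 7.7. Simulated power is 88.0% against the stated 87%.

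This reading matches the plan, so k = 1.85 at ABR 5.4 is carried forward.

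**2. Order of magnitude.** If patient rates follow a gamma distribution with relative variance k, patients drawn in proportion to their bleeding have a mean rate 1 + k times the population mean. That is 2.85 at k = 1.85 and 2.0 at k = 1.0.

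**3. Simulation of the titration.** From the protocol: 30 patients, 4-month staggered entry, main part ending at the last patient's week 24, the 2-week run-in, the 5.3.1 rule with the step at the next scheduled visit, and stopping at 0.25 mg/kg under the same count. Assumed: 60% of bleeds spontaneous, and a gamma patient effect constant over time.

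Rate ratio 0.20 vs 0.15 mg/kg, one record per dose period (median; CI coverage; share of trials showing significant harm):

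| ABR, k | True ratio | 17.5 model | With shared patient effect |
|---|---|---|---|
| 5.4, 1.85 | 1.0 | 3.11; 57%; 43% | 1.01; 95%; 4% |
| 5.4, 1.85 | 0.7 | 2.18; 63%; 9% | 0.70; 96%; 0% |
| 5.4, 1.85 | 0.5 | 1.45; 68%; 1% | 0.49; 96%; 0% |
| 8, 1.0 | 1.0 | 2.21; 51%; 49% | 1.05; 95%; 3% |
| 8, 1.0 | 0.7 | 1.52; 59%; 7% | 0.73; 97%; 0% |
| 8, 1.0 | 0.5 | 1.13; 56%; 1% | 0.55; 97%; 0% |

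With one record per patient classified by last dose (k = 2.0), the ratio is 4.4 with no true effect, significantly harmful in 76% of trials, and about 4.2 when the truth is 0.5.

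For both steps together, a repeat simulation gives about 3.2 and 4.1 (0.20 and 0.25 vs 0.15) with no effect, and about 1.6 and 1.4 when the truth is 0.5 and 0.25.

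**4. PK/PD slope per log concentration.** The footnote in 5.2 puts typical exposure at about 25%, under 40% and under 70% of a common reference. Taking the upper bounds, the ratios are 1 : 1.6 : 2.8 (0.40/0.25 and 0.70/0.25). The between-patient log-SD is assumed.

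| Log-SD | True slope | Last value, all bleeds | Per dose period | Per period with patient effect |
|---|---|---|---|---|
| 0.4 | 0 | +1.08 | +0.64 | 0.01 |
| 0.4 | −0.5 | +0.97 | +0.14 | −0.41 |
| 0.4 | −1.0 | +0.70 | −0.54 | −0.93 |
| 0.8 | 0 | +0.43 | +0.19 | 0.00 |
| 0.8 | −0.5 | +0.06 | −0.35 | −0.46 |
| 0.8 | −1.0 | −0.43 | −0.88 | −0.94 |
| 1.2 | 0 | +0.22 | +0.13 | 0.01 |
| 1.2 | −0.5 | −0.26 | −0.46 | −0.49 |
| 1.2 | −1.0 | −0.84 | −1.01 | −1.00 |

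Without a patient effect, 17 of the 18 estimates lie on the harmful side of the truth. Of the 12 with a truly protective slope, 4 change sign and 8 stay protective.

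**The case against.** Four points can be made for the plan.

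**Layout and pairing are not stated.** A reader might infer that 17.5 treats a patient's dose periods as independent and sets last-dose values against all bleeds. The protocol says neither. If 17.5 followed the end-dose data cut of the first proof-of-concept criterion, clustering and mispairing would fall away. Selection would not: the higher doses would still hold only patients who had bled.

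**Higher exposure need not look harmful.** A reader might infer that it will. The protocol's own premises are a steep response, wide variability between patients, and bleeding mainly at low concentrations. Under these the slope usually stays protective and is only weakened. Reversal needs modest exposure variability or a shallow true slope.

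**Decision weight is limited.** A reader might take 17.5 as the dose guidance. Only the PK/PD analysis is described as possibly guiding dose selection, and 17.8 refers to the main-part reporting as a whole. Section 17.5 does not decide proof of concept, and 5.2 already says doses with clearly distinct efficacy could not be chosen.

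**The remedy is not free of bias.** Its recovery of the truth above is partly built in, because the data were generated with a constant gamma patient effect. If a patient's rate also varies over 8-week blocks (assumed relative variance 0.5 or 1.0, ABR 6, 33 patients, no dose effect), the shared-effect model gives 0.96 and 0.84, or 0.89 and 0.66, for 0.20 and 0.25 vs 0.15 mg/kg. It shows a false significant benefit at 0.25 in 10% or 28% of runs. Escalating after a cluster of bleeds is followed by regression to the mean.

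All four points stand as limits. None removes the confounding in the per-dose ABRs.

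**Conclusion.** The point holds for the dose factor in either record layout. With no true dose effect, the 0.20 vs 0.15 mg/kg ratio is about 3 to 4 at the plan's ABR of 5.4, and about 2.2 at ABR 8 with k = 1.0. With one record per dose period, a true halving is hidden or mildly reversed (1.13 to 1.45). Coverage in that layout is 57-68% at ABR 5.4 and 51-59% at ABR 8. When the true benefit is strong, the main risk there is a concealed benefit, since significant false harm occurs in only about 1% of trials.

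For PK/PD, the supported statement is a bias toward harm in most settings, larger if last values are paired with all bleeds.

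The figures rest on assumptions outside the protocol: the 60% spontaneous share, k from 1.0 to 2.0, the true ratios and slopes, and exposure log-SD from 0.4 to 1.2. The direction of the dose bias follows from the escalation rule itself. The consequence is for dose and exposure interpretation before phase 3, not for proof of concept, so this should be changed but does not threaten the primary conclusion.

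**What to change.** In 17.5:

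- Model bleeds per dose period with offset log(time at that dose) and one patient-level random effect (gamma or normal) shared across the patient's periods. Report dose rate ratios with intervals.
- Pair each PK/PD value with bleeds from the same dose period, under the same patient effect.
- Label any unadjusted per-dose ABR as not comparable between doses, and state the record layout.
- Describe the rate ratios as supportive and exploratory, not as the sole dose guidance.

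**Cost.** A wording change and a random-effects count model in standard software. Escalation decisions and bleed times are already recorded (8.1.9.4, 8.3.1). Only visits 2, 9 and 16 are fixed as pre-dose for the concizumab assay (8.5.2.8), so a trough for an earlier dose period may need a model-predicted value.

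**Downside, to be stated with the results.** On average about 3 patients reach 0.25 mg/kg in simulation. The se of the log ratio is about 0.43, so the interval spans a factor of exp(1.96 × 0.43) ≈ 2.3 each way. Regression to the mean after a cluster of bleeds can still favour the higher dose.

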17.6 Secondary endpoints

17.6.1 Supportive secondary efficacy endpoints

- The number of bleeding episodes during 76 weeks from treatment onset.
- The number of spontaneous bleeding episodes during at least 24 weeks from treatment onset.
- The number of spontaneous bleeding episodes during 76 weeks from treatment onset.

The supportive secondary endpoints will be estimated using the same negative binomial regression model as the primary endpoint.

17.6.2 Supportive secondary safety endpoints

- Number of treatment-emergent adverse events (TEAEs) during at least 24 weeks from treatment onset
- Number of TEAEs during 76 weeks from treatment onset.
- Occurrence of anti-concizumab antibodies during at least 24 weeks from treatment onset.
- Occurrence of anti-concizumab antibodies during 76 weeks from treatment onset.
- Change from baseline of fibrinogen during 24 weeks from treatment onset.
- Change from baseline of fibrinogen during 76 weeks from treatment onset.

Protocol
 Trial ID:NN7415-4255
 UTN:U1111-1179-3872
 EudraCT no.:2016-000614-29

~~CONFIDENTIAL~~

Date: 18 December 2017
 Version: 3
 Status: Final
 Page: 103 of 124

Novo Nordisk

- Change from baseline of D-dimer during 24 weeks from treatment onset.
- Change from baseline of D-dimer during 76 weeks from treatment onset
- Change from baseline of prothrombin fragment 1 + 2 (F1 + 2) during 24 weeks from treatment onset.
- Change from baseline of F1 + 2 during 76 weeks from treatment onset.
- Change from baseline of prothrombin time (PT) during 24 weeks from treatment onset.
- Change from baseline of PT during 76 weeks from treatment onset.
- Change from baseline of activated partial thromboplastin time (APTT) during 24 weeks from treatment onset.
- Change from baseline of APTT during 76 weeks from treatment onset.
- Change from baseline of antithrombin (AT) during 24 weeks from treatment onset.
- Change from baseline of AT 76 weeks from treatment onset.

Adverse Events will be coded using the most recent version of Medical Dictionary for Regulatory Activities (MedDRA) coding.

A Treatment Emergent Adverse Event (TEAE) is defined as an event that has onset from the first exposure to treatment until the last visit in the trial. Treatment-emergent adverse event endpoints will be summarised by system organ class, preferred term, seriousness, severity and relation to trial product. All Adverse events will further be listed.

Frequency of binding anti-concizumab antibodies will be listed and summarised by time frame according to the two endpoint definitions.

All laboratory safety endpoints will be plotted by time, both as absolute values and change from baseline. Laboratory safety endpoints will further be summarised and listed.

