8.1.9 Treatment period - Main part

8.1.9.1 Visit 2 (Assessment, 1st concizumab treatment at site)

Visit 2 should be scheduled 14 to 21 days after visit 1. The date of visit 2 will be considered as trial day 1.

Before any concizumab administration it is important to verify the in/exclusion criteria again and review central laboratory test results from screening.

The patient must be in a non-bleeding state at the time of first administration with concizumab and should not have received any FVIII treatment for prophylaxis or for treatment of a bleeding episode within a period of 48 hours prior to dosing.

Patients will be asked to complete the ePRO questionnaires before any other trial related activities are performed according to section [8.6.1](#);

- Hemo-TEM,
- SF-36v2,
- SDS,
- TSQM,
- SIAQ-ISRQ

All protocol assessments must be performed before 1st administration of concizumab. Vital signs must be assessed both before and after concizumab administration.

Assessment results from concomitant medication, vital signs, Body measurements (weight only) and details of adverse events must be entered into the eCRF.

Protocol
 Trial ID:NN7415-4255
 UTN:U1111-1179-3872
 EudraCT no.:2016-000614-29

~~CONFIDENTIAL~~

Date:	18 December 2017	Novo Nordisk
Version:	3	
Status:	Final	
Page:	46 of 124	

At this, the 1st treatment visit, the allocated dose of concizumab will be given. Concizumab will be administered at the trial site supervised by medically trained trial staff.

The time point at which the completion of the first dose takes place corresponds to Time on treatment = 0 and must be recorded in the eCRF.

The patient must be observed at the trial site for at least 2 hours after the administration of the first dose of concizumab.

In order to determine the correct amount of the patient's daily dose of concizumab, until next scheduled visit, investigator will consult the dosing-table in the TMM on basis of the patient's current body weight.

Investigator will communicate any the daily dose of concizumab to the patient and record the dose for the coming home treatment period in the eCRF.

Prior to the first dose a dispensing call must be performed in the IWRS.

At the visit the patient will be provided with trial product (concizumab and if necessary rFVIII (turoctocog alfa)) and injection kits as well as an eDiary device to be able to conduct and report home treatment until the next scheduled visit.

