8.2.2 Concomitant illness and medical history other than haemophilia

A **concomitant illness** is any illness, other than haemophilia A, that is present at the start of the trial (i.e. at the first visit) or found as a result of a screening procedure or other trial procedures performed before first exposure to trial product. All concomitant illnesses should be reported in the Concomitant illness forms in the eCRF except information on haemophilia A which is to be reported in the Haemophilia Medical history section of the eCRF.

Medical history is a medical event, other than haemophilia A, which the patient has experienced in the past. Only relevant medical history should be reported. The information collected for concomitant illness and medical history should include diagnosis, date of onset and date of resolution or continuation, as applicable. Any change to a concomitant illness should be recorded during the trial. A clinically significant worsening of a concomitant illness must be reported as an AE.

It must be possible to verify the patient's medical history in source documents such as patient's medical record:

If a patient is not from the investigators own practice; the investigator must make a reasonable effort to obtain a copy of the patient's medical record from relevant party e.g. primary physician. See section [6.2](#) and [6.3](#) for full description of the selection criteria. The investigator must document any attempt to obtain external medical information by noting the date(s) when information was requested and who has been contacted.

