12.2 Reporting of adverse events

All events meeting the definition of an AE must be collected and reported. This includes events from the first trial-related activity after the patient has signed the informed consent until the end of the post-treatment follow-up period (visit 17). The events must be recorded in the applicable eCRF forms in a timely manner, see timelines below and [Figure 12-1](#)

During each contact with the trial site staff, the patient must be asked about AEs and technical complaints, for example by asking: “Have you experienced any problems since the last contact?”

All AEs, either observed by the investigator or patient, must be reported by the investigator and evaluated. All AEs must be recorded by the investigator on an AE form. The investigator should report the diagnosis, if available. If no diagnosis is available, the investigator should record each sign and symptom as individual AEs using separate AE forms.

For SAEs, a safety information form must be completed in addition to the AE form. If several symptoms or diagnoses occur as part of the same clinical picture, one safety information form can be used to describe all the SAEs.

AESIs regardless of the seriousness, must be reported using the AE form and safety information form

Protocol
 Trial ID: NN7415-4255
 UTN: U1111-1179-3872
 EudraCT no.: 2016-000614-29

~~CONFIDENTIAL~~

Date: 18 December 2017 | **Novo Nordisk**
 Version: 3
 Status: Final
 Page: 87 of 124

For all non-serious AEs, the applicable forms should be signed when the event is resolved or at the end of the trial at the latest.

Timelines for initial reporting of AEs:

The investigator must complete the following forms in the case report form (CRF)/eCRF within the specified timelines:

- **SAEs:** The AE form **within 24 hours** and the safety information form **within 5 calendar days** of the investigator's first knowledge of the SAE.

[figure not shown]
Both forms must be signed within 7 calendar days from the date the information was entered in the eCRF.

For SAEs requiring reporting on a specific event form: In addition to the above the specific event form within **14 calendar days** from the investigator's first knowledge of the AE.

- **Non-serious AEs fulfilling the AESI criteria:** The AE form and safety information form **within 14 calendar days** of the investigator's first knowledge of the event.

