8.5.2.7 Anti-concizumab antibodies

Sampling will be performed at all visits except at visit 3. Samples will be collected pre-dose at visit 2, 9 and 16.

Assessment of binding antibodies against concizumab (anti-drug antibodies (ADA)) will be performed at specialised laboratories whereas assessment of neutralising antibodies will be performed at Novo Nordisk A/S.

Analysis for ADA will be done as listed in [Table 2-1](#), with a bridging ECL assay (binding ADA assay), using labelled concizumab for antibody capture and detection. If a sample is confirmed positive in the confirmatory assay, the sample is considered antibody positive. Confirmed positive samples will be characterised for binding to IgG backbone, CDR region or the S241P mutation. Furthermore, positive samples will be characterised for neutralising activity using a modified TFPI functionality assay (neutralising ADA assay). All antibody assays are validated according to international guidelines and recommendations.

The following analyses will be available:

Protocol
 Trial ID:NN7415-4255
 UTN:U1111-1179-3872
 EudraCT no.:2016-000614-29

~~CONFIDENTIAL~~

Date:	28 December 2017	Novo Nordisk
Version:	4.0	
Status:	Final	
Page:	67 of 124	

- Anti-concizumab antibody assay
- Specificity assay (Anti-concizumab antibodies cross reacting with IgG4 backbone, CDR region or S241P mutation)
- Anti-concizumab neutralising antibody assay

Samples will be drawn at all visits except at visit 3. The samples will be analysed in batches during the trial and results will be available to the data monitoring committee approximately every third month after the first patient has been dosed (Section [12](#)). Neutralising antibodies will be analysed and reported at the end of trial. A detailed description of the assay methods will be included in the antibody analysis report at the end of the trial.

Investigators will be notified in case their patient is shown to have developed neutralising antibodies against concizumab.

Samples for the determination of anti-drug antibodies collected during the treatment period must be drawn prior to administering trial products.

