12.2 Reporting of adverse events

All events meeting the definition of an AE must be collected and reported. This includes events from the first trial-related activity after the patient has signed the informed consent until the end of the post-treatment follow-up period (visit 17). The events must be recorded in the applicable eCRF forms in a timely manner, see timelines below and [Figure 12-1](#)

During each contact with the trial site staff, the patient must be asked about AEs and technical complaints, for example by asking: “Have you experienced any problems since the last contact?”

All AEs, either observed by the investigator or patient, must be reported by the investigator and evaluated. All AEs must be recorded by the investigator on an AE form. The investigator should report the diagnosis, if available. If no diagnosis is available, the investigator should record each sign and symptom as individual AEs using separate AE forms.

For SAEs, a safety information form must be completed in addition to the AE form. If several symptoms or diagnoses occur as part of the same clinical picture, one safety information form can be used to describe all the SAEs.

AESIs regardless of the seriousness, must be reported using the AE form and safety information form

Protocol
 Trial ID: NN7415-4255
 UTN: U1111-1179-3872
 EudraCT no.: 2016-000614-29

~~CONFIDENTIAL~~

Date: 28 December 2017 | **Novo Nordisk**
 Version: 4.0
 Status: Final
 Page: 87 of 124

For all non-serious AEs, the applicable forms should be signed when the event is resolved or at the end of the trial at the latest.

Timelines for initial reporting of AEs:

The investigator must complete the following forms in the case report form (CRF)/eCRF within the specified timelines:

- **SAEs:** The AE form **within 24 hours** and the safety information form **within 5 calendar days** of the investigator's first knowledge of the SAE.

[figure not shown]
Both forms must be signed within 7 calendar days from the date the information was entered in the eCRF.

For SAEs requiring reporting on a specific event form: In addition to the above the specific event form within **14 calendar days** from the investigator's first knowledge of the AE.

- **Non-serious AEs fulfilling the AESI criteria:** The AE form and safety information form **within 14 calendar days** of the investigator's first knowledge of the event.

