The investigator must ensure that the recording of the worst case severity and seriousness of an event is kept throughout the trial. A worsening of an unresolved AE must be reported as follow up with re-assessment of severity and/or seriousness of the event.

Queries or follow-up requests from Novo Nordisk must be responded to **within 14 calendar days** from the date of receipt of the request, unless otherwise specified in the follow-up request.

SAEs after end of trial: If the investigator becomes aware of an SAE with a suspected causal relationship to the investigational medicinal product occurring to a patient after the patient has ended the trial, the investigator should report this SAE within the same timelines as for SAEs during the trial.

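### The TEAE definition leaves out adverse events that begin between consent and first dose and then worsen on concizumab

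*Protocol*

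**What the plan says.** All references are to the protocol.

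- **Definition.** Section 17.6.2 says that a TEAE "is defined as an event that has onset from the first exposure to treatment until the last visit in the trial". It has no clause for worsening.
- **Collection.** Section 12.2 requires all AEs to be reported: "This includes events from the first trial-related activity after the patient has signed the informed consent until the end of the post-treatment follow-up period".
- **Pre-dose window.** Section 8.1.9.1: "Visit 2 should be scheduled 14 to 21 days after visit 1".
- **Worsening of an AE.** Section 12.3: "A worsening of an unresolved AE must be reported as follow up with re-assessment of severity and/or seriousness of the event". The same section has the worst severity and seriousness kept on the record.
- **Worsening of a concomitant illness.** Section 8.2.2: "A clinically significant worsening of a concomitant illness must be reported as an AE". A concomitant illness is one present at the first visit, or one that trial procedures bring to light before first exposure.

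The number of TEAEs is called a key secondary endpoint in the summary and a supportive secondary endpoint in sections 4.2.2.1 and 17.6.2.

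**The concern.** A single-arm trial has no control group against which to judge adverse events, so the TEAE count carries much of the safety summary. That count is meant to hold what appeared or got worse under treatment. A definition by onset alone captures only what appeared. Whether worsening is captured then depends on how it is recorded. If it opens a new AE, the new onset date falls on treatment and the event counts. If it updates an old AE, the old onset date stands and the event does not count. Section 12.3 takes the second route. An event that is mild in screening and severe on concizumab would then be missing from the TEAE tables by severity, seriousness and relation to trial product.

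**Working it through.** The question is one of definitions, and the plan states no figure to reproduce. The rules are applied in turn to three kinds of pre-dose condition, each of which worsens after the first dose.

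**1. Illness present at visit 1, or found by a trial procedure before dosing.** Section 8.2.2 makes it a concomitant illness. Its clinically significant worsening is reported as an AE in its own right, with onset on treatment. It counts as a TEAE.

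**2. Event that arises between visit 1 and first dose and is reported by the patient.** It was not present at visit 1 and was not found by a procedure, so section 12.2 makes it an AE with pre-dose onset. If it is unresolved and worsens on drug, section 12.3 makes that follow-up on the same AE. Onset remains before first exposure, and section 17.6.2 excludes it. It does not count. Because the record keeps the worst grade and section 12.3 asks for no date of worsening, an analyst relying on that record could not tell whether the worst grade came before or after the first dose.

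**3. Abnormal laboratory result in the visit 2 sample.** Haematology is sampled at every visit except visit 3 (section 8.5.2.2), and section 8.1.9.1 places all visit 2 assessments before the first dose. Section 8.5.2.2 has an abnormal result seen after screening reported as an AE; sections 8.5.2.3 and 8.5.2.5 say the same for biochemistry and coagulation. Section 12.1.1 says that conditions found by trial procedures before exposure are not AEs. Under the laboratory sections the finding follows route 2 and a later worsening is not counted. Under section 12.1.1 it follows route 1 and the worsening is counted. The same result can be classified either way.

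**Scale, for illustration only.** The documents give the number dosed (33) and the window (14 to 21 days), but no AE rate and no share that worsens.

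- Pre-dose time: 33 × 2/52 = 1.27 to 33 × 3/52 = 1.90 patient-years.
- Assume 2 to 6 AEs per patient-year: 1.27 × 2 = 2.5 to 1.90 × 6 = 11.4 screening AEs.
- Assume 5% to 20% of them are unresolved and worsen on drug: 2.5 × 0.05 = 0.1 to 11.4 × 0.20 = 2.3 events in the trial.
- If AEs arise at the same rate before and after dosing, that rate cancels when missed events are compared with TEAEs of the first 24 weeks: 2/24 × 5% = 0.4% to 3/24 × 20% = 2.5%.

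The assumed rates have no basis in the documents, so these ranges show an order of magnitude and are not estimates.

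**The case against.** The case against the point has several parts.

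- *Concomitant illness is already covered.* This stands, and it removes the largest group. A reader might infer that any pre-dose condition aggravated by concizumab is missed; sections 8.2.2 and 12.1.1 show that this is not so. If trial procedures were read broadly enough to include asking the patient at visit 2, route 2 would also be covered, but the AE collection from consent in section 12.2 would then have little left to collect.
- *Nothing is lost.* This stands for case reporting. Section 17.6.2 lists all AEs, and section 12.3 requires an AE that becomes serious to be reported within 24 hours. A reader might infer that serious events could go unseen; the documents do not support that. Only the TEAE count is affected.
- *The count is descriptive.* True: no test depends on it.
- *The SAP may define TEAEs differently.* It might, but the protocol states the definition itself. An SAP also cannot supply a date of worsening that was never collected.
- *The quoted text is version 3.* Version 4.0 is dated ten days later, and its section 17 is not shown, so the current TEAE wording cannot be confirmed. The worsening rule in section 12.3 is unchanged in version 4.0.

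**Conclusion.** The point holds in a narrow form. Under the protocol's own rules, an AE that starts between consent and first dose, is not a concomitant illness, and worsens on concizumab is left out of the TEAE endpoint. The number is probably small and cannot be sized from the documents. The conclusion assumes that section 17.6.2 reads in version 4.0 as it does in version 3.

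A reader might infer that the antibody endpoint has the same fault and counts antibodies present before dosing. The documents do not say so. The endpoint runs from treatment onset, so the samples from visit 1 and from visit 2 before dosing lie outside it. The sentence "If a sample is confirmed positive in the confirmatory assay, the sample is considered antibody positive" is a laboratory rule for a sample and not a rule for counting patients. Section 8.5.2.7, where it turns to patients, speaks of those who develop antibodies during the trial. The reporting sentence, "Frequency of binding anti-concizumab antibodies will be listed and summarised by time frame according to the two endpoint definitions", is silent on patients positive before dosing. That is a derivation detail an SAP would commonly settle, and the pre-dose samples needed for it are collected.

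**What to change.** - In section 17.6.2, define a TEAE as an event with onset, or an increase in severity or seriousness of an event already present, after first exposure and up to the last visit.
- In section 12.3, require the date on which an AE with pre-dose onset worsens after the first dose.
- Reconcile the laboratory sections (8.5.2.2, 8.5.2.3, 8.5.2.5) with section 12.1.1, so that an abnormal result in the pre-dose visit 2 sample has one classification.
- Check whether section 17 of version 4.0 carries the same definition, and amend that text.

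The cost is a few sentences and one date field, with no new visits or samples. The TEAE count may rise slightly.
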